4.13.4 Vital Signs

A by-patient listing of all vital sign measurements (including weight) and change from baseline will be presented.

Baseline is defined in section 4.2.4.

Measured (observed) values including changes from baseline will be summarized by cohort/ treatment and time point and by vital sign parameter (BP (systolic and diastolic [mmHg]), pulse rate(bpm), respiratory rate (breaths per minute), and body temperature (tympanic [ear] or non-contact infrared thermometers) (°C)).

Measurements obtained at screening will not be included in the tabulations of descriptive statistics.

4.13.5 ECG

Standard safety 12-lead ECGs will be performed as shown in the section 6.1.

The following ECG parameters will be recorded:

PR interval (msec)

QRS interval (msec)

RR interval (msec)

QT interval (msec)

QT interval corrected using the Fridericia correction formula (QTcF) (msec).

The ECG will be evaluated by the Investigator as 'Normal', 'Abnormal, NCS' or 'Abnormal, CS'.

All ECG parameters will be listed by each patient and time point including changes from baseline.

Baseline is defined in section 4.2.4.

Descriptive statistics for observed values and changes from baseline will be presented by cohort and treatment group. A categorical QTc analysis will also be performed.

Measurements obtained at Screening will not be included in the shift tables and in the tabulations of descriptive statistics.

Measurements obtained prior to dosing in each period will be included in the tabulations for the treatment received in that specific treatment period.

A summary of the number and percentage of patients with QT/QTc intervals exceeding some predefined upper limits (eg, >450 msec, >480 msec, >500 msec for measured values as well as. >30 msec, >60 msec for changes from baseline) of ECG parameters (QT interval, QTcF and QTcB) will be displayed in a frequency table.

The listing of ECG abnormality will be presented separately.

4.13.6 Physical Examination

Physical examinations will be performed as shown in the section 6.1.

The full physical examination includes an assessment of general appearance and a review of systems (dermatologic, head, eyes, ears, nose, mouth/throat/neck, thyroid, lymph nodes, respiratory, cardiovascular, gastrointestinal, extremities, musculoskeletal, neurologic and psychiatric systems).

The brief physical examination includes an assessment of the general appearance, skin, abdomen, cardiovascular system and respiratory system.

Abnormal physical examination findings will be listed.

4.13.7 Other Analysis

Not Applicable

4.13.8 Exploratory Analysis

The following disease activity parameters for RA will be listed and summarized by descriptive statistics and displayed graphically as appropriate.

- American College of Rheumatology (ACR) 20/50/70 response criteria
- Disease activity score 28 (DAS28)
- Clinical disease activity index (CDAI)
- Simplified disease activity index (SDAI)

The derivation of the above endpoints is as follow:

elements	CDAI	SDAI	DAS28 CRP	DAS28 ESR	ACR
Swollen Joint Count (SJC)	Х	Х	Х	Х	Х
Tender Joint Count (TJC)	Х	Х	Х	Х	Х
Patient Global Assessment (PGA or Patient global score)	Х	Х	Х	Х	Х
Evaluator Global Assessment (EGA or Provider global score)	Х	Х			Х
CRP (mg/L)		Х	Х		x (or ESR)
ESR (mm/hr)				Х	x (or CRP)
Pain VAS					Х
HAQ					Х

Baseline (Day 1), Current value (Day 7) and CFB (Day 1 - Day 7) and %CFB ((Day 1-Day7)/Day1*100) of Disease activity data elements (numbers of SJC and TJC, PGA, EGA, CRP, ESR, pain VAS and HAQ-DI) scores will be summarized using the n, mean, SD, minimum,

median, and maximum by cohort, treatment and overall, on Exploratory Population. %CFB will be presented only for two decimal places.

A by-patient disease activity data elements (numbers of SJC and TJC, PGA, EGA, CRP, ESR, pain VAS and HAQ-DI) scores will be listed based on Exploratory population

American College of Rheumatology

ACR CRP Response Criteria: A Patient is considered as ACR 20 (50/70) responder if

- At least 20%(50% / 70%) improvement in SJC(28 Joint count) compared to baseline, AND
- At least 20%(50% / 70%) improvement in TJC(28 Joint count) compared to baseline, AND
- At least 20%(50% / 70%) improvement in 3 out of following five measures
 - 1. Patient's assessment of pain on VAS(0-10)
 - 2. Patient's global assessment (PGA or Patient global score) of the disease (0-10)
 - 3. Evaluator global assessment (EGA or provider global score) of the disease (0-10)
 - 4. Patient's assessment of disability on HAQ
 - 5. Acute phase reactant (C-reactive Protein (CRP))

ACR ESR Response Criteria: A Patient is considered as ACR 20 (50/70) responder if

- At least 20% (50% / 70%) improvement in SJC(28 Joint count) compared to baseline, AND
- At least 20% (50% / 70%) improvement in TJC(28 Joint count) compared to baseline, AND
- At least 20%(50% / 70%) improvement in 3 out of following five measures
 - 1. Patient's assessment of pain on VAS(0-10)
 - 2. Patient's global assessment (PGA or Patient global score) of the disease (0-10)
 - 3. Evaluator global assessment (EGA or provider global score) of the disease (0-10)
 - 4. Patient's assessment of disability on HAQ
 - 5. Acute phase reactant (Erythrocyte sedimentation rate (ESR))

ACR 20/50/70 (ESR and CRP) will be summarized using count and percentage of responders by cohort and treatment on Exploratory Population. The percentages of ACR20, (50, or 70) responders are calculated by the equation, "number of ACR20 (50, or 70) responders / number of subjects on each cohort x 100 (%)" by each cohort.

A by-patient listing of percentage of responders of ACR 20/50/70 (ESR and CRP) will be presented on Exploratory Population

Health Assessment Questionnaire - Disability Index (HAQ-DI)

The HAQ-DI consists of eight categories of functioning expressed through 20 questions. Activities are organized under the categories of Dressing & Grooming, Arising, Eating, Walking, Hygiene, Reach, Grip, and Activities. Each item is scored on a 4-point scale from 0 to 3, representing Without ANY Difficulty [0], With SOME Difficulty [1], With MUCH difficulty [2], and UNABLE to do [3].

Scoring for the eight functional categories and overall disability index scoring will be performed as follows:

There are eight categories including 20 items; first score within each category:

- Dressing and Grooming, includes 2 items
- Arising, includes 2 items
- Eating, includes 3 items
- Walking, includes 2 items
- Hygiene, includes 3 items
- Reach, includes 2 items
- Grip, includes 3 items
- Activities, includes 3 items

The score for each category will be the single response within the category with the highest score (greatest difficulty).

For example, in the "Eating" category, there are two answers (one for each item). If " Use chopsticks by yourself" is marked as "3" and "Lift a full cup or glass to your mouth" is marked as "0", then the score for the "Eating" category would be "3" (the response indicating the greatest difficulty within the category). If a component question is left blank or the response is too ambiguous to assign a score, then the score that that category will be determined by the remaining completed question(s). However, if any "aids or devices" and/or "help from another person" items at the bottom of each page are checked with the exception of "other", the category to which they apply will be adjusted upward to "2". If the basic score is already "2" or "3", the score remains unchanged. "Aids or devices" and "help from another person" can only change a category's score to "2"; they do not change the score to a "1" or a "3". Companion aids/devices items for HAQ-DI categories are presented in Table 4-3. No score will be adjusted, if only other is ticked, regardless of the specification.

The score for the disability index will be the mean of the eight category scores. If more than two of the categories, or 25%, are missing, scale will not be scored. If fewer than 2 of the categories are missing, divide the sum of the categories by the number of answered categories. The higher score indicates greater disability.

 Table 4-3 Companion aids/devices items for HAQ-DI categories

HAQ-DI Companion Item

Dressing & Grooming	Devices used for dressing (button hook, zipper
	pull, long-handled shoe horn, etc.)
Arising	Special or built up Chair
Eating	Built up or special utensils
Walking	Cane, Walker, Crutches, Wheelchair
Hygiene	Raised toilet seat, Bathtub seat, Bathtub bar,
	Long-handled appliances in bathroom
Reach	Long-handled appliances for reach
Grip	Jar opener (for jars previously opened)

Disease activity score 28 (DAS28)

DAS28 ESR
 0.56× √(TJC)+0.28× √(SJC)+0.7×LN(ESR)+0.14*×(PGA)
 DAS28 CRP
 0.56× √(TJC)+0.28× √(SJC)+0.36×LN((CRP)+1) +0.14*×(PGA)

+0.96

*Because PGA data in this study are collected with 0-10 scale, instead of 0-100 scale, this coefficient is 0.14, not 0.014 usually found in the formula. LN means log natural.

Clinical disease activity index (CDAI)

 $\circ \quad CDAI = SJC + TJC + PGA + EGA$

Simplified disease activity index (SDAI)

$$\circ$$
 SDAI = SJC + TJC + PGA + EGA + 0.1*CRP

Baseline (Day 1), Current value (Day 7), CFB (Day 1 - Day 7) and %CFB ((Day 1 – Day7)/Day1*100) of DAS28 ESR, DAS28CRP, CDAI, and SDAI will be summarized using the n, mean, SD, minimum, median, and maximum by cohort, treatment and overall, on Exploratory Population. %CFB will be presented only for two decimal places.

If any of the elements are missing, then the corresponding parameter will be considered as missing.

A by-patient disease activity data parameters (DAS28 ESR, DAS28CRP, CDAI, and SDAI) scores will be listed based on Exploratory population.

For Exploratory Biomarker refer section 4.15.

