1.1		Updated dose strength to 175 mg throughout the document Update the unit of CRP from mg/dL to mg/L, accordingly, SDAI = SJC + TJC +PGA + EGA + 0.1*CRP DAS 28 CRP = $0.56 \times \checkmark$ (TJC) + $0.28 \times \checkmark$ (SJC) + $0.36 \times LN((CRP)+1) + 0.14* \times (PGA) + 0.96$ Added line in section 4.13.8 "If any of the elements are missing, then the corresponding parameter will be considered as missing." to handle the parameter in case of missing elements. Removed inactive URL link of DAS28 ESR	
20	Date of last signature	Final	

LIST OF ABBREVIATIONS

Abbreviation/Acronym	Definition/Expansion	
ACR	American College of Rheumatology	
AE	Adverse event	
Ae	Amount of study drug excreted unchanged in the urine	
AESI	Adverse events of special interest	
ALT	Alanine aminotransferase	
AST	Aspartate aminotransferase	
AUC	Area under the curve	
AUC _{0-inf}	Area under the plasma concentration-time curve from pre- dose (time 0) extrapolated to infinite time	
AUC _{0-t}	Area under the plasma concentration-time curve up to last measurable concentration	
AUC _{tau}	Area under the plasma concentration-time curve over a dosing interval	
BDRM	Blinded data review meeting	
BL	Biostatistician Lead	
BLQ	Below the lower limit of quantification	
BMI	Body mass index	
BP	Blood pressure	
bpm	Beats per minute	
CCL2	C-C motif chemokine ligand 2	
CDAI	Clinical disease activity index	
CI	Confidence interval	
CL/F	Apparent total body clearance, determined for parent only	
Clast	Last observed quantifiable concentration at tlast	
CLr	Renal clearance of drug from plasma	
C _{max}	Maximum plasma concentration determined directly from the concentration-time profile	
COMP	Cartilage oligomeric matrix protein	
CPMS	Clinical Pharmacology, Modeling, and Simulation	

Abbreviation/Acronym	Definition/Expansion	
CS	Clinically significant	
CSR	Clinical Study Report	
Ctrough	Concentration in a dosing period defined as the pre-dose concentration of the day	
CTCAE	Common Terminology Criteria for Adverse Events	
CV	Coefficient of variation	
CXCL10	C-X-C motif chemokine ligand 10	
DAS28	Disease activity score 28	
DRM	Data Review Meeting	
ECG	Electrocardiogram	
eCRF	Electronic case report form	
EGA	Evaluator Global Assessment (Provider global score)	
EOS	End of study	
Fe	Percentage of study drug excreted unchanged in the urine	
Fe%	Urinary cumulative excretion as % of unchanged drug	
GM-CSF	Granulocyte macrophage colony stimulating factor	
HAQ	Health Assessment Questionnaire	
HBc	Hepatitis B core	

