4.2.6 Summary and Representation of Data

Continuous data will be summarized by cohort and treatment group using descriptive statistics (number, mean, standard deviation, minimum, median, and maximum).

Categorical data will be summarized by cohort and treatment group using frequency tables (number and percentage.

The minimum and maximum will be reported to the same number of decimal places as the raw data recorded in the database. The mean and median will be reported to one more decimal place than the raw data recorded in the database. The SD will be reported to two more decimal places than the raw data recorded in the database. In general, the maximum number of decimal places reported shall be four for any summary statistics.

Percentages will be presented to one decimal place for safety outputs and two decimal places for exploratory outputs. Percentages will not be presented for zero counts. Percentages will be calculated using N as the denominator. If sample sizes are small, the data displays will show the percentages, but any textual report will describe frequencies only. Percentage will be presented as whole number if count is 100.

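### The any-missing-element rule in SAP 4.13.8, read as covering ACR20/50/70, sets to missing results that the available elements already decide; its scope needs stating (low priority).

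*SAP*

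**What the plan says.** SAP 4.13.8 opens with "The following disease activity parameters for RA will be listed and summarized by descriptive statistics". The first entry in that list is "American College of Rheumatology (ACR) 20/50/70 response criteria"; DAS28, CDAI and SDAI follow. A table of elements then gives each index a column. The ACR column marks swollen and tender joint counts (SJC, TJC), patient and evaluator global assessments, CRP or ESR, pain VAS and HAQ.

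ACR response has three parts. Both joint counts are mandatory; the first condition reads "improvement in SJC(28 Joint count) compared to baseline, AND", and TJC has the same form. The third part asks for "improvement in 3 out of following five measures". The SAP derives an ACR-CRP version and an ACR-ESR version separately.

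After the DAS28, CDAI and SDAI formulas comes the missing-data sentence: "If any of the elements are missing, then the corresponding parameter will be considered as missing". The SAP Revision History says it was added "to handle the parameter in case of missing elements", with no exception for ACR.

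The ACR percentage divides the responders by the "number of subjects on each cohort x 100". SAP 4.2.6 adds: "Percentages will be calculated using N as the denominator". No other text covers a missing ACR element. SAP 4.17 bars imputation apart from partial dates, and the HAQ-DI text deals only with gaps inside that questionnaire.

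**The concern.** DAS28, CDAI and SDAI are sums in which every term is needed, so a missing term properly makes the score missing. ACR is a counting rule, and one absent measure often cannot alter the answer. A patient who meets both joint counts and three of the four available measures is a responder whatever the fifth would have been. A patient who fails a joint count is a non-responder whatever else is absent.

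If the sentence applies to ACR, both patients become missing. Because the denominator is not reduced, a missing result is printed in effect as a non-response. The certain non-responder makes no difference to the percentage, but the certain responder lowers it. In cohorts this small, one such patient visibly moves a rate that the exploratory objective asks for.

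**Working it through.** The plan gives no figure on this point to reproduce. The check enumerates the SAP's own rule.

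**Inputs**
- Rule (SAP 4.13.8): response = SJC met AND TJC met AND at least 3 of 5 measures met. The same logic applies at the 20%, 50% and 70% thresholds.
- Cohort (SAP 3.1): 8 patients, 6 active and 2 placebo.
- Denominator (SAP 4.13.8 and 4.2.6): subjects, not available results.

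**Step 1. Which results are already decided?** Each available element is met or not met. A pattern is decided if every possible value of the missing element(s) gives the same answer.

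With one of the five measures missing, six elements remain, giving 2^6 = 64 patterns:
- SJC or TJC not met: 3 × 16 = 48 patterns, all certain non-responders.
- Both joint counts met: 16 patterns of the four available measures. Three or four met: 4 + 1 = 5 certain responders. None or one met: 1 + 4 = 5 certain non-responders. Exactly two met: 6 undetermined.
- Total: 5 certain responders, 48 + 5 = 53 certain non-responders, 6 undetermined.

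The other cases follow in the same way:

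| Missing | Patterns | Certain responder | Certain non-responder | Undetermined |
|---|---|---|---|---|
| 1 of 5 measures | 64 | 5 | 53 | 6 |
| 2 of 5 measures | 32 | 1 | 25 | 6 |
| 3 of 5 measures | 16 | 0 | 12 | 4 |
| SJC or TJC | 64 | 0 | 48 | 16 |

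If the sentence covers ACR, none of these patterns keeps a result. Certain responders are lost only in the first two rows. The counts describe logic, not frequency; patterns are not equally likely.

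**Step 2. Effect on the printed rate.** A certain non-responder set to missing leaves numerator and denominator unchanged. A certain responder set to missing lowers the numerator by one:
- Denominator 6 (active patients at one dose): 1/6 = 16.7 points. For example, 3/6 = 50.0% prints as 2/6 = 33.3%.
- Denominator 8 (whole cohort, the literal wording): 1/8 = 12.5 points. For example, 3/8 = 37.5% prints as 2/8 = 25.0%.

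**Step 3. How often a gap would hide a responder.** The documents give neither response rates nor missingness rates, so this is an assumed range. Suppose both joint counts are met, one measure is missing, and each other measure improves independently with probability p. Then P(certain responder) = 4p³(1 − p) + p⁴:

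| p | P(certain responder) |
|---|---|
| 0.1 | 0.4% |
| 0.3 | 8.4% |
| 0.5 | 31.3% |
| 0.7 | 65.2% |

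These figures must still be multiplied by the chance of meeting both joint counts. If that chance equals p, then 0.3 × 8.4% = 2.5%, 0.5 × 31.3% = 16% and 0.7 × 65.2% = 46%. All are conditional on a measure being missing in the first place.

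**The case against.** The strongest reply concerns scope. The missing-data sentence follows the summary text for DAS28-ESR, DAS28-CRP, CDAI and SDAI and precedes a listing sentence that names those same four scores as parameters. ACR's own summary and listing text ends well before, ahead of the HAQ-DI section. The Revision History records the line in the same entry as the SDAI and DAS28-CRP formula changes. Read that way, the rule is right and discards nothing for ACR.

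This stands as a possible reading, so a reader should not infer that the SAP certainly discards ACR responders. It does not remove the point. The section's opening list and element table both include ACR, the sentence has no exception, and on the narrow reading ACR has no missing-element rule at all. Two programmers could produce different tables.

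Other parts of the reply also stand:
- Little missing data is likely. Both assessments, Days 1 and 7, fall within the in-house stay (Protocol 4.1 and Table 1-1), and CRP is in the safety chemistry panel drawn on both days. HAQ-DI tolerates some missing items.
- A missing CRP affects only ACR-CRP and a missing ESR only ACR-ESR, so the other version survives. A missing pain, global or HAQ score affects both.
- Element scores are listed by patient, so a lost response could be recovered by hand.
- High improvement rates have no support in the documents. Protocol 2.3.2 expects no benefit to patients from such short treatment, and the second assessment comes before the Day 7 dose.

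**Conclusion.** The point holds as a low-priority correction. As written, the sentence most naturally reaches ACR20/50/70, and there it replaces decided results with missing ones. The printed rate can only fall as a result: 16.7 points per lost certain responder with 6 in the denominator, 12.5 with 8. The SAP wording does not settle which denominator applies.

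This rests on three conditions: the broader reading of the sentence, a denominator that keeps patients with missing ACR, and at least one otherwise certain responder with one or two of the five measures missing. The documents give no basis for saying how often the last occurs.

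Two stronger inferences are not supported. A reader might take the 58 of 64 decided patterns (5 + 53) as the size of the error, but 53 are non-responders whose loss leaves the percentage unchanged. A reader might also infer a bias against TCK-276 relative to placebo. The same rule applies to both, no missingness by arm is given, and nothing establishes a direction for that contrast. The endpoint is exploratory and descriptive, with no hypothesis test, and dose escalation rests on safety, tolerability and PK.

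**What to change.** Limit the sentence in SAP 4.13.8 to DAS28-ESR, DAS28-CRP, CDAI and SDAI. For ACR20/50/70, in both the CRP and ESR versions, add:

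- Responder: SJC, TJC and at least 3 available measures meet the threshold.
- Non-responder: SJC or TJC fails, or fewer than 3 measures could meet the threshold even if every missing one is counted as met.
- Missing: only if the available elements do not determine the result.

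This keeps results that follow from observed data. It imputes nothing and does not conflict with SAP 4.17. State at the same time whether the ACR denominator is the treatment group within a cohort or the whole cohort.

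The cost is a few sentences and a small programming change, with no new data. As the SAP is final, the change belongs in the Statistical Method Modification Form that SAP section 1 provides for.

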4.13.9 Daylight Saving Time (DST)

Not Applicable

4.13.10 Safety Monitoring (Independent Data Monitoring Committee, Data Monitoring Committee, Data and Safety Monitoring Board)

A SRC will be appointed for this study. The SRC meeting will take place to review safety and PK data during each dose level. The SRC will evaluate the safety and tolerability data up to Follow-up/EOT Visit and available PK data up to Day 10 to determine the next dose for the subsequent cohort.

The SRC will review available blinded safety, tolerability, and PK data after each cohort to confirm whether it is safe to proceed with the next planned dose, whether the dose escalation should be stopped, or if the dose should be lowered, repeated or titrated in the subsequent cohort.

4.14 Cardio Dynamic Analyses

Not Applicable

4.15 Biomarkers

Descriptive statistics for observed values, changes from baseline and % changes from baseline, and a by-patient listing will be provided for the following biomarkers based on Exploratory Population. This data will also be displayed graphically as appropriate.

Biomarker	Description	Read out*					
MMP-3	Matrix metalloprotei	nase-3					
GM-CSF	Granulocyte mac	ophage colony					
	stimulating factor						
CXCL10	C-X-C motif chemok	ine ligand 10					
CCL2	C-C motif chemokine	C-C motif chemokine ligand 2					
COMP	Cartilage oligomeric	Cartilage oligomeric matrix protein					
TNF-α	Tumor necrosis facto	Tumor necrosis factor - α					
TNF-RI	Tumor necrosis facto	Tumor necrosis factor-RI					
IL-6	Interleukin-6	Interleukin-6					

* Biomarker name exactly as it will appear in the dataset

Handling of LLOQ and ULOQ

Biomarker data are reported as concentration results, measured using a specific assay with a working range defined by the two limits: Lower limit of quantification (LLOQ) and Upper limit of quantification (ULOQ). Values which fall below the LLOQ or above the ULOQ are reported as < LLOQ * dilution factor (dilution factor: if sample diluted and concentration measured still below LLOQ) and > ULOQ * dilution factor, respectively.

To ensure that biomarkers only have numerical values, censored values will be imputed as follows

- Values below the LLOQ are replaced by LLOQ/2.
- Values above the ULOQ are replaced by ULOQ.

Imputed values are used for summary statistics, inferential analyses and plots (with a special symbol). Values below LLOQ and values above ULOQ are shown as such in the listings. In the

summary table, the frequency (n, %) of values below the LLOQ and above the ULOQ, respectively, will be included.

If the proportion of imputed data is more than 20% for any treatment group at any time point, a footnote is added to the summary statistics table stating that the proportion of values outside the limits of quantification is more than 20% for some treatment groups at some time points and that in such cases summary statistics may be heavily biased.

If the proportion of imputed data for a given biomarker, across all treatment groups and time points, is more than 50%, no summary statistics will be provided, and the data are only listed.

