Exploratory 
● To evaluate the effect of TCK-276 on disease activity and biomarkers in patients with RA	
● Exploratory endpoints 
The following exploratory disease activity parameters for RA will be assessed:
 
○ American College of Rheumatology (ACR) 20/50/70 response criteria○ Disease activity score 28 (DAS28)○ Clinical disease activity index (CDAI)○ Simplified disease activity index (SDAI) 
The following exploratory biomarkers will be assessed:
 
○ Matrix metalloproteinase-3 (MMP-3)○ Granulocyte macrophage colony-stimulating factor (GM-CSF)○ C-X-C motif chemokine ligand 10 (CXCL10)○ C-C motif chemokine ligand 2 (CCL2)○ Cartilage oligomeric matrix protein (COMP)○ Tumor necrosis factor (TNF)-alpha○ TNF-R1○ Interleukin-6 (IL-6)

4 Study Design

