3 INVESTIGATIONAL PLAN

3.1 Overall Study Design and Plan

This is a Phase 1, multi-center, double-blind, randomized, placebo-controlled, multiple ascending dose (MAD) study to evaluate the safety, tolerability, and pharmacokinetics (PK) of orally administered TCK-276 in both males and females with RA. Blood samples for possible future pharmacogenetic, possible future metabolite assessments, and possible future pharmacodynamic (PD) assessments will be collected.

A total of thirty-two (32) patients with RA will be enrolled in this clinical study. This MAD study will consist of 4 cohorts of 8 patients (6 active treatment and 2 matching placebo, or a 3:1 ratio), each receiving an oral dose of TCK-276 or matching placebo for 7 days (once daily [QD] under fed condition). Each cohort will be divided into 2 subgroups to implement the sentinel dosing approach. Within each cohort, the first subgroup will consist of 2 sentinel patients; one patient will receive TCK-276, and one patient will receive matching placebo. The second subgroup will consist of 6 patients (5 active treatment, 1 matching placebo). Individual patients in the second subgroup will be dosed at least 72 hours after the first subgroup following a decision by the Investigators based on all available safety data from the sentinel patients up to 48 hours post-dose.

Dose group	Treatment Assignment	
1	10 mg TCK-276 (N = 6)	Placebo $(N = 2)$
2	25 mg TCK-276 (N = 6)	Placebo $(N = 2)$
3	75 mg TCK-276 (N = 6)	Placebo $(N = 2)$
4	175 mg TCK-276 (N = 6)	Placebo $(N = 2)$

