4.2 General Presentation Considerations

This section is not applicable to PK data.

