4.12.1 Pharmacokinetic Concentrations

Concentration Listings:

Pharmacokinetic Plasma concentration data for TCK-276 and TEI-W00595, will be listed by cohort/treatment/Day and patient for the PKAS. Concentration listings will include nominal PK sampling time, actual sampling times relative to dose administration, deviation from nominal time, and percent deviation from nominal time, and concentrations. Plasma concentrations below the lower limit of quantification (LLOQ) will be presented as below the limit of quantification (BLQ) in the listings and the LLOQ value presented as a footnote. Missing PK samples will be reported as no sample (NS) or not reportable (NR) as appropriate and considered excluded from PK analysis.

Concentration Summary Tables:

Source data as reported from the laboratory will be used for calculation of concentration summary statistics. Tabular summaries for concentration-time data will report N (number of patients in PKAS), n (number of patients with non-missing values), and n(BLQ) (the number of patients with BLQ samples).

Concentration for TCK-276 and TEI-W00595 will be summarized by cohort/treatment/Day, and nominal timepoint for the PKAS. The following descriptive statistics will be presented for plasma concentrations obtained at each nominal time point: N, n, n(BLQ), arithmetic mean, SD, coefficient of variation (CV%), geometric mean, geometric CV% (calculated as: $gCV\% = SQRT(e^{s^2}-1)*100$; where s is the SD of the log-transformed values), median, minimum, and maximum values.

For summary concentration tables, all BLQs will be considered zero, and the number of BLQs and quantifiable concentrations at each scheduled time point will be reported. Summary Statistics will not be calculated if quantifiable concentrations at a scheduled time point is <3 and will be reported as not calculated (NC).

The rules followed for calculation and presentation of concentration data with regards to the number of decimal places/significant digits for the listings of patient level concentrations and summary tables of concentration are as follows:

Concentration Listings and Tables	Rounding
Individual concentrations (Listings)	n s f. as supplied by bioanalytical laboratory
Minimum and Maximum	n s f. as supplied by bioanalytical laboratory
Mean/SD/Median/Geomean	3 s.f.
CV%/gCV%	1 d.p.
N/n	Whole number

s f = significant figures, d.p. = decimal place

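### SAP 4.15 plans no geometric mean ratio or interval for the biomarkers and leaves the sign of % change undefined; the mean % change can understate a fall

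*SAP*

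**What the plan says.** The exploratory objective (Protocol Section 3, Table 3-1; SAP 2.3) is "To evaluate the effect of TCK-276 on disease activity and biomarkers in patients with RA". Biomarker blood is drawn before dosing on Day 1 and again on Day 7. The design is "4 cohorts of 8 patients (6 active treatment and 2 matching placebo, or a 3:1 ratio".

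SAP 4.15 asks for "Descriptive statistics for observed values, changes from baseline and % changes from baseline" without naming the statistics. SAP 4.2.6 names them: "Continuous data will be summarized by cohort and treatment group using descriptive statistics (number, mean, standard deviation, minimum, median, and maximum". SAP 4.2 opens with "This section is not applicable to PK data", so only PK data are exempt and the list governs the biomarkers. Protocol 9.3.1 gives the same list. SAP 4.2.1 includes pooled placebo among the treatments.

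SAP 4.15 also says that "a by-patient listing will be provided for the following biomarkers based on Exploratory Population" and that "This data will also be displayed graphically as appropriate". Values below LLOQ become LLOQ/2. A biomarker with more than 50% imputed values is listed only. The section says that imputed values feed inferential analyses, but specifies none.

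For PK concentrations the SAP does use log-scale statistics; 4.12.1 lists "coefficient of variation (CV%), geometric mean, geometric CV" alongside the arithmetic ones.

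The SAP uses two sign conventions for change. Section 4.13.8 (disease activity) subtracts Day 7 from Day 1, so a fall is positive. Section 4.13.3 (laboratory data) subtracts baseline from the later value, so a fall is negative. Section 4.15 gives no formula.

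**The concern.** Biomarker concentrations are positive, and their within-patient ratios are often right-skewed. A patient whose value doubles counts as +100%, and one whose value halves counts as -50%, although the two are equal and opposite on the ratio scale. The arithmetic mean of % changes therefore estimates the mean ratio, which lies above the typical ratio. A real reduction looks smaller than it is, and with no effect the mean shows a rise.

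Protocol 2.1 says the results will inform the design and dose selection of later studies. For that use, a reader needs an estimate of the size of the change and some statement of its precision. The plan gives no precision for any biomarker estimate. Where the mean and median disagree, it does not say which one to read. With the sign undefined, the direction of a printed change is also open to misreading.

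**Working it through.** The plan states no SD, effect size or power for biomarkers, so it has no figure of its own to reproduce beyond 4 × (6 + 2) = 32 patients, of whom 4 × 2 = 8 form pooled placebo.

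**Inputs.** n = 6 per dose (SAP 3.1). Assumed: a lognormal Day 7/Day 1 ratio, true geometric mean ratio G = 0.7 (a 30% fall), and log-ratio SD s from 0.2 to 1.0. Percent change is taken as (Day 7 - Day 1)/Day 1.

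**Formulas.** The expected arithmetic mean % change is 100 × (G × exp(s²/2) - 1). At s = 0.5 this is 0.7 × exp(0.125) - 1 = 0.7 × 1.133 - 1 = -20.7%. At s = 0.7 it is 0.7 × exp(0.245) - 1 = 0.7 × 1.278 - 1 = -10.6%. The chance that the geometric mean shows no fall is Φ(ln G/(s/√6)). The other entries come from 400,000 simulated groups of 6. Each cell gives the expected % change, then the chance that the statistic shows no fall.

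| s | Mean (planned) | Median (planned) | Geometric mean (not planned) |
|---|---|---|---|
| 0.2 | -28.6%; <0.1% | -29.6%; <0.1% | -29.8%; <0.1% |
| 0.3 | -26.8%; 0.6% | -29.1%; 0.6% | -29.4%; 0.2% |
| 0.5 | -20.7%; 11.7% | -27.5%; 6.6% | -28.5%; 4.0% |
| 0.7 | -10.6%; 29.9% | -24.9%; 14.9% | -27.0%; 10.6% |
| 1.0 | +15.4%; 51.3% | -19.3%; 24.4% | -24.0%; 19% |

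**No effect (G = 1).** The expected mean % change is exp(s²/2) - 1: +2.0%, +4.6%, +13.3%, +27.8% and +64.9% for the same values of s.

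**Break-even.** The expected mean shows no fall when s = √(2 ln(1/G)): 0.84 for a 30% fall and 0.67 for a 20% fall.

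**Sample size.** At s = 0.5 the expected mean is about -20.7% at n = 6, 8, 24 and 100. The geometric mean moves from -28.5% at n = 6 to -29.9% at n = 100. The shift in the mean comes from skewness; small n adds noise.

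**Sign.** With (Day 1 - Day 7)/Day 1 the same expected means print as +20.7% and +10.6% against a true +30%. The fall is understated under either convention.

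**An example with no assumed SD.** Of 6 patients, one goes from below LLOQ (imputed as LLOQ/2) to LLOQ, +100%. One goes the other way, -50%. Four are unchanged. The mean is (100 - 50)/6 = +8.3%. The geometric mean ratio is (2 × 0.5)^(1/6) = 1, and the median is 0. At each time point 1/6 = 16.7% of this group is imputed, so the group does not trigger the SAP's 20% footnote.

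**The case against.** The strongest reply is that the planned table already contains most of what is needed. The median stands beside the mean. At s = 0.5, 0.7 and 1.0 it lowers the chance of showing no fall from 11.7%, 29.9% and 51.3% to 6.6%, 14.9% and 24.4%, which is most of the way to the geometric mean. The range, the listing and any graphs would expose a single extreme patient. This stands, and it rules out a reading that a reader might infer: that the biomarkers are summarised by arithmetic means alone, so that a real fall would go unseen.

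The pooled placebo column also helps. With equal s, both columns are inflated by the same factor: at s = 0.7, 0.894/1.278 = 0.70 recovers the true ratio. This holds only for a reader who divides. Subtracting the printed means gives -10.6 - 27.8 = -38.4 points, which overstates a 30% fall. No interval accompanies either comparison.

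A reader might also infer that 6 patients per dose cause the bias, or that it is always upward. Neither follows: the expectation does not contain n, and the direction depends on a sign that 4.15 leaves open.

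Finally, the protocol states no hypotheses (9.1) and plans descriptive exploratory analysis (9.3.4.1). Escalation uses safety, tolerability and PK (Protocol 7.1.2; SAP 4.13.10), and geometric means can be computed later from the collected data. All of this is true, and it limits the severity. It does not supply the missing interval or sign.

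**Conclusion.** The point holds as a minor one. SAP 4.15 has no geometric or log-ratio summary, no interval and no definition of % change for the biomarkers. Where ratios are right-skewed, the mean % change understates a fall at any n. For a true 30% fall the shortfall is about 1 to 3 percentage points at s = 0.2 to 0.3, about 9 at s = 0.5 and about 19 at s = 0.7. The expected mean hides the fall completely only at s of about 0.84 or more.

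These sizes rest on an assumed lognormal ratio and assumed SDs, and they ignore imputation at the LLOQ and ULOQ. Actual skewness may differ among the eight biomarkers.

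The documents do not support saying that the exploratory objective is left without a usable estimate. The median is planned and lies close to the geometric result at moderate s. What it lacks is an interval, and at n = 6 it is noisier than the geometric mean.

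**What to change.** In SAP 4.15, for each biomarker:

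- Add the geometric mean and geometric CV% by day, in the form already used for PK concentrations in 4.12.1.
- Add the geometric mean ratio Day 7/Day 1 with 95% CI, for each dose and for pooled placebo.
- Define % change as (Day 7 - Day 1)/Day 1, so that a fall is negative, and give the absolute change the same sign.
- Keep the median, range, listing and the 50% imputation rule.
- Either specify the inferential analyses mentioned or remove the reference.

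Optionally, add one ANCOVA of ln(Day 7) on ln(Day 1) and treatment, reported as ratio to pooled placebo with 95% CI and labelled exploratory. It would give 8 × 4 = 32 contrasts of 6 against 8 patients with no multiplicity plan, so it is not essential.

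The cost is SAP wording and one table from data already collected. The intervals will be wide. With n = 6 and a sample log SD of 0.5, the half-width is 2.571 × 0.5/√6 = 0.525 on the log scale, a factor of exp(0.525) = 1.69. An observed ratio of 0.70 would then have a 95% CI from 0.70/1.69 = 0.41 to 0.70 × 1.69 = 1.18. The planned summary does not show this uncertainty.
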